PROTOCOL and SAP

The Role of Human Fibrinogen Concentrate (RiaSTAP) in Decreasing Blood Loss and the Need for Component Blood Therapy in Infants Undergoing Cardiopulmonary Bypass

National Clinical Trial (NCT) Identification Number: NCT02822599

December 7, 2017

Purpose of Study

The goal of the study is to determine whether the use of Human Fibrinogen Concentrate (RiaSTAP) will decrease blood loss and the need for component blood therapy in neonates and infants undergoing cardiopulmonary bypass. RiaSTAP will be administered after termination of Cardiopulmonary Bypass (CPB) at a dose of 70 mg/kg, in a prospective, randomized, controlled study. We hypothesize that the administration of RiaSTAP in this manner will reduce peri-operative bleeding and transfusion requirements.

Background

Severe postoperative bleeding is a serious complication after cardiac surgery and results in increased morbidity and mortality¹². The bleeding is often multifactorial and influenced by both surgical factors and impaired hemostasis. The impaired hemostasis after cardiac surgery may be caused by enhanced fibrinolysis, platelet (PLT) dysfunction and coagulopathy secondary to the exposure of blood to artificial surfaces, and the surgical trauma³.

In children less than 12 months old with congenital heart disease, bleeding after cardiac surgery is further complicated as the fibrinogen of these patients is qualitatively dysfunctional⁴. Moreover, the coagulation systems of neonates and children undergoing CPB are profoundly affected by hemodilution⁵ and by consumption⁶. As a result, neonates and young infants undergoing complex cardiac repairs often receive multiple units of blood products, both in the operating room (OR) and intensive care unit (ICU).

Preoperative fibrinogen concentration is an independent predictor of post-operative bleeding volume. Fibrinogen concentration, even when within the normal range, is a limiting factor for post-operative hemorrhage⁷. The prophylactic infusion of fibrinogen concentrate has been shown to reduce bleeding after coronary artery bypass graft (CABG) surgery without evidence of hypercoagulability⁸. Moreover, ROTEM FIBTEM test guided fibrinogen concentrate administration was associated with reduced transfusion requirements and 24 hour postoperative bleeding in patients undergoing aortic valve operations and ascending aortic reconstructions⁹.

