Patients under 10 kg in body weight will have the CPB pump primed with one unit of Packed Red Blood Cells (PRBC) and 200 cc Fresh Frozen Plasma (FFP). In patients over 10 kg a pure crystalloid prime will be used. Target hemoglobin (Hg) while on CPB will be 9 gm/dL, but the transfusion trigger for additional units of PRBC will be 7 gm/dL.

Drug protocol:

The following laboratory studies will be obtained prior to surgery: Complete Blood Count (CBC), Prothrombin time (PT), International Normalized Ratio (INR), Partial Thromboplastin time (PTT), Platelet count, and a Fibrinogen level; an electrolyte profile will also be done. An Activated Clotting Time (ACT) and a Thromboelastometry analysis [REDACTED], a device that assesses the viscoelasticity of whole blood and other parameters, will be done after an A-line is placed (Figure 1).

A blood products transfusion algorithm was developed based on four previous studies published in the literature, modified for pediatrics¹⁶¹⁷¹⁸¹⁹ (Figure 2). Blood is measured in the cell saver reservoir and the suction canister every fifteen minutes while in the OR. Clinically significant bleeding, requiring treatment, will be defined as a rate in excess of 10 cc/kg/hr calculated every 15 minutes while in the OR. Calculations will be done every 60 minutes in the CICU.

After rewarming, but prior to the termination of CPB a ROTEM analysis will be done. Platelets or FFP will be administered at this time, while still on CPB, if the ROTEM results indicate a deficiency of either component. Then immediately after the termination of CPB, RiaSTAP or NS will be administered depending on the group assignment. Then, as per routine care, a ROTEM analysis and fibrinogen level will be assessed and the transfusion algorithm will be continued. *If the ROTEM indicates a fibrinogen deficiency, cryoprecipitate will be given.* Thereafter, as per routine care, a ROTEM analysis will be done at least every 30 minutes while in the OR or sooner at the discretion of the OR team. Once the patient leaves the OR a ROTEM will be done at least every 60 minutes for the first six hours or until clinically significant bleeding has stopped, whichever comes first; ROTEMs can be done more frequently at the discretion of the ICU staff caring for the patient. The blood products transfused after separation from CPB will be based on the protocol below (Figure 3). Dosing amounts of the required component therapy will be based on the formula below:

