PRBC: Volume required = Blood volume (V) x desired Hct increase / Hct of red cell unit (70%)

FFP: 20 cc/kg

Plateletpheresis: 20 cc/kg

Cryoprecipitate: 10 cc/kg

The ROTEM analysis algorithm is below (Figure 4).

Four main scenarios based on clinical observation and TEM results were possible:

1. Insignificant bleeding—normal TEM \Rightarrow no transfusions
2. Insignificant bleeding—abnormal TEM \Rightarrow no transfusions
3. Significant bleeding—normal TEM \Rightarrow surgical reevaluation
4. Significant bleeding—abnormal TEM \Rightarrow transfusion of blood products as indicated by:
 - a. fib-TEM MCF < 7 mm \Rightarrow cryoprecipitate
 - b. hep-TEM MCF < 50 mm \Rightarrow platelets,
 - c. hep-TEM CT > 240 seconds \Rightarrow FFP,
 - d. hep-TEM CFT > 110 seconds \Rightarrow cryoprecipitate and /or platelets depending on MCF

If clinically indicated (continuing bleeding) or to verify the treatment effect and control heparin reversal, a second set of in-TEM, hep-TEM, and fib-TEM analyses will also be performed during wound closure. ACT will be tested in all patients to control for heparin reversal. If patients have both a pathological ACT and TEM, protamine will be administered.

Postoperative bleeding in the ICU will be defined as the total amount of chest tube drainage after closure of the sternum and during the first 24 postoperative hours. If the sternum is not closed, it will be defined as the total chest tube drainage during the first 24 postoperative hours. An intensive care nurse blinded to group assignment will record the bleeding every hour. The amount of transfused red blood cells (RBC), FFP, cryoprecipitate and platelets during the hospital stay will be recorded in cc/kg. The transfusion triggers will be as described above. The CICU physicians and nurses will not be informed of the preoperative fibrinogen concentration or group assignment.

Patient Assessment:

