line thrombosis. These include edema, leg pain and tenderness, erythema, and discoloration for venous thrombosis, as well as loss of distal peripheral pulses, pain, pallor, paresis, paresthesias, decreased skin temperature for arterial thrombosis. If any of these signs and symptoms appear, Doppler Ultrasound examinations of the affected area will be performed.

The Safety Team, which consists of the Cardiac Intensive Care Unit physicians, will evaluate each event when it occurs; they will not be blinded to patient assignment after 24 hours. Please see safety assessments and timing below. These represent minimums as prescribed by the protocol. Assessments may be more frequent (See table 1).

Stopping Criteria:

A statistically significant increase in thromboembolic phenomenon between Group 1 and Group 2 will trigger a stop in enrollment. This will be monitored by the Safety Team.

Table 1: Assessments

Assessment	Timing in OR	Timing in ICU
EBL	q 15 min	hourly
ROTEM	q 30 min as needed	hours 2 and 24, or as needed hourly until bleeding ceases
peripheral thromboembolism	N/A	q8 hrs, or as needed
hemoglobin	as needed	hours 2 and 24
PT/PTT, platelets, fibrinogen	prior to surgery if not previously done	hours 2 and 24

Schedule of Events

	Pre-Operative	Intraoperative	2 hours Post-Operative	24 hours Post-Operative	When occurs	60 ± 14 days
Informed Consent/Assent	x					
Eligibility Assessment	x					

Demographic Data	X					
Medical History	X					
Baseline Assessment ¹	X					
Body Weight and Height	X					
Concomitant Medications ⁴	X	X				
Randomization		X				
Administration of Study Drug		X				
Pharmacy Prep of Study Drug		X				
Laboratory Studies ²	X		X	X		
Adverse Events		X	X	X	X	X
Surgical and Cardiopulmonary Bypass Data ³		X				
Estimated Blood loss (EBL) ^{5,6}					→	
ROTEM Analysis ^{9,11}	X	X ^{7,10}	X	X	X ⁸	
Identification of total transfused blood products ¹²				X		
Thromboembolic Assessment ¹³			→		X	
Factor VII					X	
Length of Stay ICU and Hospital					X	
Mechanical ventilation duration					X	
Need for Re-exploration first 12 hours			X	X		
Phone assessment						X

1. Assessment includes allergies, diagnosis, procedure(s)
2. Laboratory collection and assessment includes CBC, prothrombin time (PT), international normalized ratio (INR), partial thromboplastin time (PTT), fibrinogen level. Pre-Operative includes complete platelet count, and electrolyte profile.

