To avoid selection bias, patients will be randomized to their treatment assignment group by the research pharmacists using the Research Randomizer. The randomization procedures are detailed in the Methods and Procedures section of this protocol. All operating room and ICU personnel will be blinded to the patient's Group assignment. An intensive care nurse blinded to group assignment will record postoperative bleeding every hour. Since the study is blinded and the practitioners caring for the patient will not know if the subject received the study drug or placebo, for the study treatment period (ending 24 hours after surgery), the Cardiac Intensive Care Unit staff will monitor the incidence of adverse thromboembolic events and intervene with routine care, if necessary. In order to maintain patient safety, the ROTEM analyses must be interpreted by the anesthesiologist caring for the patient in order to guide transfusion therapy. This is the standard of care and an integral part of the protocol. The hospital staff anesthesiologists are also investigators in the study including the Principal Investigator. As part of routine care, if the ROTEM results indicate a deficiency of platelets or FFP, either component will be administered while still in the OR. In addition, if the ROTEM indicates a fibrinogen deficiency after termination of CPB, cryoprecipitate will be given. After review of the ROTEM values, the identity of the study drug may be discernable. In order to avoid the ascertainment bias from this knowledge, study data will be analyzed by a biostatistician independent of the investigator prior to any presentation or publication of study results. The biostatistician will be blinded to the study treatment assignment.

Statistical Analyses

All quantitative measures will be analyzed using descriptive statistics [mean +/- standard deviation (SD), etc.]. Treatment and placebo group comparisons will be made with the Student's t-test (continuous variables) or Fisher's exact test (categorical variables). A p-value of ≤ 0.05 will be considered statistically significant. For group comparisons of variables that will be analyzed at more than onetime point, Analysis of Variance (ANOVA) for repeated measurements will be used followed by Student's t-test if the ANOVA (group or interaction between group and time) indicated a statistically significant difference ($p \leq 0.05$).

Data Storage and Confidentiality

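### The 24-hour bleeding and the 2 h and 24 h laboratory comparisons use no baseline covariate, although the pre-op values are collected; the tests are valid, but some precision and protection against chance imbalance is given up

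*Combined protocol and SAP*

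**What the plan says.** - **Statistical Analyses.** For measures compared once: "Treatment and placebo group comparisons will be made with the Student's t-test (continuous variables". For variables analysed at more than one time: "Analysis of Variance (ANOVA) for repeated measurements will be used", followed by t-tests if the group or the group-by-time term is significant. No covariate, change score or regression model is named, and the time levels are not listed.
- **Endpoints.** Bleeding over the first 24 hours (cc/kg) is a single value, so the t-test applies. Hemoglobin and the hemostasis panel are listed at 2 h and 24 h, so the ANOVA applies.
- **Background.** "Preoperative fibrinogen concentration is an independent predictor of post-operative bleeding volume". The same section says of infants with congenital heart disease that "the fibrinogen of these patients is qualitatively dysfunctional".
- **Drug protocol.** "The following laboratory studies will be obtained prior to surgery": the list includes CBC, PT, INR, PTT, platelets and fibrinogen. A thromboelastometry analysis follows arterial-line placement, and a ROTEM follows rewarming, before the study drug. At the end of the section: "The CICU physicians and nurses will not be informed of the preoperative fibrinogen concentration or group assignment".
- **Schedule of Events.** Laboratory studies are marked pre-op, at 2 h and at 24 h; the footnote reads "Laboratory collection and assessment includes CBC, prothrombin time (PT), international normalized ratio (INR), partial thromboplastin time (PTT), fibrinogen level". ROTEM is also marked pre-op. Table 1 times the coagulation tests "prior to surgery if not previously done".

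**The concern.** The protocol names a predictor of its bleeding endpoint, measures it before surgery and keeps it from the CICU staff, but the analysis does not use it. Each laboratory endpoint likewise has a pre-op value of the same variable that the analysis does not clearly use. The Randomization text describes no stratification, so baseline is not handled by design either. With 30 infants, precision is scarce and a chance difference in baseline fibrinogen is quite possible. An adjustment added after the results are seen would look data-driven.

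**Working it through.** **Inputs.** From the documents: 15 per group and significance at p ≤ 0.05. Sidedness is not stated; two-sided is assumed. The documents give no SD, effect size, power or correlation, so there is no planned figure to reproduce. Assumed: normal data, a true difference of 0.8 SD, and baseline-outcome correlation r from 0 to 0.5.

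**1. Bleeding, unadjusted t-test.** SE = √(2/15) = 0.365 SD. Noncentrality = 0.8/0.365 = 2.191 on 28 df, critical value 2.048. Power = 56%.

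**2. Bleeding, ANCOVA with one covariate.** SE² = (2/15)(1 − r²)(1 + 1/26) on 27 df, critical value 2.052. The factor 1 + 1/26 is the average cost of estimating the slope. The last column is simulated.

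| r | SE | 0.8/SE | Power | 95% CI width relative to t-test |
|---|---|---|---|---|
| 0 | 0.372 | 2.150 | 55% | 1.02 |
| 0.2 | 0.365 | 2.194 | 56% | 1.00 |
| 0.3 | 0.355 | 2.254 | 58% | 0.97 |
| 0.4 | 0.341 | 2.346 | 62% | 0.94 |
| 0.5 | 0.322 | 2.483 | 67% | 0.88 |

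**3. Chance imbalance.** The baseline difference between arms has SE 0.365 SD, so a difference of 0.5 SD or more occurs in about 17% of trials. At 0.5 SD it moves the unadjusted result by 0.5r: 0.15 SD at r = 0.3 and 0.25 SD at r = 0.5. In simulation, the t-test's false-positive rate in those 17% of trials is 7.5% (r = 0.3) or 12% (r = 0.5). In the other 83% it is 4.5% or 3.7%, and overall it is 5%. ANCOVA stays near 5% in both sets.

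**4. Laboratory values, only 2 h and 24 h as time levels.** The group test is then a t-test on each patient's mean of the two values. Assume 0.8 SD at both times and a 2 h-24 h correlation of 0.5. The variance of the mean is (1 + 0.5)/2 = 0.75.
- Without baseline: SE² = 0.75 × 2/15 = 0.100, noncentrality 2.530, power about 69%.
- With the own pre-op value: SE² = (0.75 − r²)(2/15)(1 + 1/26). Noncentrality is 2.483, 2.552, 2.646 and 3.040 at r = 0, 0.2, 0.3 and 0.5; power is 67%, 69%, 72% and 83%.
- With a 2 h-24 h correlation of 0.7 (variance 0.85): 63% without; 61%, 63%, 66% and 76% with.

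**5. Laboratory values, pre-op as a third time level.** The group main effect now averages in a time that treatment cannot affect. The effect falls to 0.8 × 2/3 = 0.533. At a 2 h-24 h correlation of 0.5, the variance of the three-value mean is (3 + 2 × 0.5 + 4r)/9.
- r = 0.3: variance 0.578, noncentrality 0.533/√(0.578 × 2/15) = 1.92, power 46%.
- r = 0.5: variance 0.667, noncentrality 1.79, power 41%.

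The interaction test recovers part of this. In simulation, group or interaction is significant in about 70% (r = 0.3) and 75% (r = 0.5) of trials. That either-or rule has about 10% false positives, so these figures are not comparable with those in step 4.

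**The case against.** An unadjusted primary test is a legitimate choice in a randomized trial, and for bleeding the case for changing it is thin. ANCOVA loses slightly at r = 0, breaks even at 0.2 and gains about 2 points at 0.3. The documents give several reasons to expect a low r:
- by its title, the source for the predictor statement concerns coronary bypass grafting;
- the infants' fibrinogen is described as dysfunctional;
- patients under 10 kg receive plasma in the pump prime, and FFP or platelets may be given on bypass before the study drug;
- excluding patients with a rewarming FIBTEM MCF above 15 mm may narrow the fibrinogen range.

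Skewed bleeding data do not improve the case. With lognormal data (log SD 0.6, effect 0.8 SD on the log scale, raw-scale analysis), simulated power is 49% against 51% at r = 0.3 and 49% against 58% at r = 0.5. All of this stands and limits the claim.

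For the laboratory values, it can be said that baseline may already enter as a time level, since the schedule places these tests pre-op too. The text allows that reading. A reader might infer that the plan certainly ignores the laboratory baselines; the documents do not support this, because the time levels are not listed. But a time level is not covariate adjustment, and it weakens the group main effect (step 5).

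The rewarming ROTEM, taken after dilution by the prime, may be a better covariate than the one after arterial-line placement. Both precede the study drug and either is valid, so this does not count against adjusting.

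**Conclusion.** The point holds as a worthwhile improvement, not as a defect that invalidates the analysis. A reader might infer that the unadjusted comparisons are biased or have an inflated error rate. They do not: under randomization the t-test is unbiased on average and its false-positive rate is 5% overall. A reader might also infer that the named predictor guarantees a useful power gain for bleeding. The documents give no correlation, and the gain is nil to about 2 points up to r = 0.3, reaching 6 points at 0.4 and 11 at 0.5.

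For laboratory values adjusted for their own baseline, the gain may be larger: about 14 points at r = 0.5 and 3 to 4 at r = 0.3, given a 2 h-24 h correlation of 0.5 and only those two time levels. Prime and transfusion may weaken that link as well. Apart from any gain, the unstated role of the pre-op value in the ANOVA needs to be settled. All sizes rest on 15 per arm, a 0.8 SD effect, normal data and assumed correlations.

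**What to change.** Fix the following in the Statistical Analyses section before any outcome is seen by group:
- **Bleeding.** Analyse 24-hour postoperative bleeding (cc/kg) by ANCOVA with group and one covariate, preoperative fibrinogen, defined as the last value before surgery. Keep the unadjusted t-test as a sensitivity analysis.
- **Laboratory values.** In the repeated-measures models, state that 2 h and 24 h are the only time levels. Enter each variable's own pre-treatment value as a covariate, and use the same covariate in the follow-up comparison at each time.
- **ROTEM.** Name in advance which pre-study-drug analysis supplies the covariate: after arterial-line placement or at rewarming.
- **Missing baseline.** State a rule for a missing pre-op value.

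No new data are needed. The price is one degree of freedom per model: if the covariate does not predict, about 2 power points and a 95% interval about 2% wider.

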Our institution has been using RiaSTAP on this high-risk patient population since April 2013. In a separate, retrospective analysis our group has compared a group of 50 patients who received RiaSTAP with 50 age, diagnosis and procedure matched patients prior to April 2013. Our analysis demonstrates that there is a statistically significant reduction in the need for FFP and cryoprecipitate, without an increase in thromboembolic events, when RiaSTAP is used at a dose of 70 mg/kg.¹⁵

Criteria For Subject Selection

Number of subjects: 30

Gender of subjects: There are no gender-based enrollment restrictions for this study. Gender distribution should reflect the gender distribution of the patient population and the gender distribution of Congenital Heart Disease (CHD) in general which is slightly skewed towards male patients in a 60:40 ratio of males to females.

Age of Subjects: Age will range from full term (at least 37 weeks gestational age) newborns to 12 months old, inclusive.

Racial and Ethnic Origin: There are no racial and ethnic restrictions for this study.

Inclusion Criteria: All neonatal and infant cardiac patients presenting for open-heart surgery at Nicklaus Children's Hospital will be eligible for enrollment in the study.

Exclusion criteria: Patients who fall outside of the age range for the study will be excluded. Patients known to have had an anaphylactic or severe reaction to the drug or its components will not be enrolled. At the time of the rewarming ROTEM, any patient with a FIBTEM MCF > 15 mm, will be excluded.

Vulnerable subjects: Patients in the study population are neonatal and infant cardiac surgical patients and are considered vulnerable subjects.

Methods and Procedures

Randomization:

We plan to enroll 30 neonates and infants scheduled for elective cardiac surgery. Patients will be randomized to one of two groups with 15 patients in each group; Group 1 will receive an infusion of RiaSTAP, right after the termination of CPB at a dose of 70 mg/kg and

Group 2 will receive a placebo of Normal Saline 0.9% (NS) during the same time period. The volume of NS will be calculated to be the same volume that would be used IF the patient were receiving RiaSTAP. This will be the only difference between the groups.

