Both Groups will receive the normal standard of care both before and especially after this event. This will be the only event that is different for the two groups. To avoid selection bias, the Pharmacy will perform the randomization using Research Randomizer. Briefly, for each patient, a randomly generated integer between 1-30 will be produced. If the number is even, the patient will be assigned to Group 1. If the number is odd, the patient will be assigned to Group 2. The randomization process and schedule will be provided by the Principal Investigator's office, but the actual patient assignment will be done by Pharmacy.

All operating room and ICU personnel will be blinded to the patient's Group assignment. The only persons who will have access to the identity of the Group assignment from the time of randomization until 24 hours after surgery will be members of the Pharmacy staff. NONE of these individuals will be involved in patient care. The DSMB will be unblinded AFTER the study treatment period concludes (24 hours after surgery).

Endpoints:

Primary efficacy endpoints will be estimated as follows:

- postoperative bleeding (EBL) during the first 24 hours (hr) after surgery (cc/kg),
- the identity and total volume of transfused blood products (cc/kg) given in the peri-operative period, separated out into its components,
- hemoglobin concentration 2 hr. and 24 hr. after surgery and
- effects of fibrinogen infusion on global hemostasis 2 hr. and 24 hr. after surgery (PT, PTT, INR, fibrinogen level, platelet count and ROTEM analysis).

Post-operative period begins after the patient leaves the operating room. The need for Factor VII use and dose will also be included as a primary end point. Factor VII is typically used only if there is profuse bleeding not amenable to component transfusion therapy.

Secondary end points will include:

- the number of post-op hours requiring ventilator support,
- Length of Stay (LOSH) in the hospital,
- Length of Stay (LOS ICU) in the Cardiac Intensive Care Unit (CICU) and
- the need for re-exploration for bleeding within the first 12 hours.

The primary safety endpoints that will be monitored are the presence of a clinical adverse events. Clinical adverse events (AEs) are defined as any clinical signs of central or peripheral thromboembolism, respiratory or circulatory failure, or allergic reactions during hospital stay. It will also include infection with a blood-borne pathogen.

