fib-tem®	Provides information on fibrinogen level and quality of fibrin polymerization in citrated blood by inhibiting thrombocytes	Reagent contains thrombocyte inhibitor and recalcification reagent. Used in conjunction with ex-tem® test	- Store at +2 - +8°C - Stable until the expiration on label. Vials must be used within 14 days after opening
hep-tem®	Used to monitor the coagulation process via the intrinsic pathway, in the presence of unfractionated heparin, in citrated whole blood specimens	Reagent contains heparinase that inactivates heparin in vitro. Also contains an optimized calcium ion concentration in a buffer to start the coagulation reaction	-- Store at +2-+8°C - Stable until expiration on label. - Reconstituted reagent is stable for 30 days at +2 - +8°C
in-tem®	Used to monitor the coagulation process via the intrinsic pathway in citrated whole blood specimens	Reagent contains an concentration of ellagic acid creating a standardized mild activation of the contact phase through negatively loaded surface. Sample is recalcified with a-tem®	Store at +2-+8°C - Stable until expiration on label. Vials must be used within 8 days after first opening

Figure 2 Transfusion Algorithm

ROTEM Parameters
 CT = Clotting time (sec)
 CFT = Clot formation time (sec)
 MCF = Maximal clot firmness (mm)

Figure 3. Blood Transfusion Protocol

Dosing amounts of the required component therapy will be based on the formula below:

PRBC: Volume required = Blood volume (V) x desired Hct increase / Hct of red cell unit (70%)

FFP: 20 cc/kg

[figure not shown]
Plateletpheresis: 20 cc/kg

Cryoprecipitate: 10 cc/kg

Figure 4. Rotem Experience

ROTEM® Experience

Using Detailed Hemostasis Information

Please note: Results from the ROTEM® delta should not be the sole basis for a patient diagnosis, but should be evaluated together with the patient's medical history, the clinical picture, and if necessary, further coagulation tests.

Risk/Benefit Assessment

Risk Category: Greater than minimal.

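### The planned Student's t-test pools variances although the allocation rule seldom gives equal arms; Welch's version is safer for roughly continuous endpoints, but not for volumes that are mostly zero or one fixed dose

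*Combined protocol and SAP*

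**What the plan says.** Statistical Analyses names one test for every continuous comparison: "Treatment and placebo group comparisons will be made with the Student's t-test (continuous variables) or Fisher's exact test (categorical variables". Variables measured at more than one time point first go through a repeated-measures ANOVA, "followed by Student's t-test if the ANOVA (group or interaction between group and time) indicated a statistically significant difference". The threshold is "A p-value of ≤ 0.05 will be considered statistically significant", with sidedness not stated. The section gives no unequal-variance option, variance check, transformation or rank-based alternative.

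Criteria For Subject Selection gives "Number of subjects: 30", and the Randomization text says "Patients will be randomized to one of two groups with 15 patients in each group". The rule that follows is: "Briefly, for each patient, a randomly generated integer between 1-30 will be produced", and then "If the number is even, the patient will be assigned to Group 1", with odd numbers going to Group 2. No blocking and no bar on repeated numbers is stated.

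The Drug protocol and Figure 3 set component volumes as fixed amounts per kilogram, for example "Cryoprecipitate: 10 cc/kg", with 20 cc/kg for FFP and for platelets.

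**The concern.** Pooling assumes that both arms have the same variance. When they do not, a 15:15 split largely hides the error and an uneven split exposes it. If the larger arm has the smaller variance, the pooled standard error is too small: intervals are too narrow, and tests of equal means reject too often. If the larger arm has the larger variance, the opposite happens and real effects are missed. Chance decides which case applies in the one trial that is run.

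Unequal spread is plausible if the drug works. A volume that is either zero or a fixed dose has an SD that depends on the share of infants transfused, and the drug is hypothesised to reduce transfusion. What is at stake is the calibration of standard errors, intervals and p-values for the split obtained. Skewness is a separate matter.

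**Working it through.** **Inputs.** From the documents: N = 30, planned 15:15, probability 15/30 for each arm per infant, threshold 0.05. Assumed: two-sided tests, independent draws, normal data unless stated, and control:treated SD ratios of 1.5 and 2. The documents give no effect size, SD or power, so there is no sample-size figure to reproduce; the figure to check is the 15:15 split.

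**1. The split.** Under Binomial(30, 0.5), P(15:15) = C(30,15)/2^30 = 155,117,520/1,073,741,824 = 14.4%. So P(unequal arms) = 85.6%. P(17:13 or worse) = 58.5%, P(18:12 or worse) = 36.2%, P(20:10 or worse) = 9.9%.

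**2. The standard error.** The pooled form uses s² = [(nT − 1)σT² + (nC − 1)σC²]/28 and SE = √[s²(1/nT + 1/nC)]. The true value is √(σT²/nT + σC²/nC). Take σT = 1 and σC = 2:

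- 18 treated:12 control: s² = (17 + 44)/28 = 2.179. Pooled SE = √(2.179 × 0.1389) = 0.550; true SE = √(1/18 + 4/12) = 0.624. Ratio 0.88.
- 12:18: s² = (11 + 68)/28 = 2.821. Pooled SE = 0.626; true SE = √(1/12 + 4/18) = 0.553. Ratio 1.13.
- 15:15: s² = (14 + 56)/28 = 2.5. Both SEs are 0.577. Ratio 1.

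**3. Rejection rates for equal means** (numerical integration, agreeing with simulation):

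| Treated:control | Student, ratio 1.5 | Student, ratio 2 | Welch, both ratios |
|---|---|---|---|
| 20:10 | 8.6% | 11.4% | 5.1% |
| 18:12 | 7.1% | 8.6% | 5.0-5.1% |
| 17:13 | 6.4% | 7.4% | 5.0-5.1% |
| 15:15 | 5.1% | 5.3% | 5.0% |
| 13:17 | 4.1% | 3.7% | 4.9-5.0% |
| 12:18 | 3.6% | 3.0% | 4.9-5.0% |
| 10:20 | 2.7% | 1.9% | 4.9% |
| Average over splits | 5.3% | 5.7% | 5.0% |

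For normal data, the rejection rate at equal means equals the non-coverage of the 95% interval at any true difference. The table therefore also describes intervals when the drug does have an effect.

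**4. A fixed-dose example.** Assume one 20 cc/kg dose in 50% of controls and 10% of treated infants. SD = D√[p(1 − p)]: 20 × √0.25 = 10 and 20 × √0.09 = 6. The means are 10 and 2 cc/kg. Coverage of the pooled 95% interval is 91% at 18:12, 89% at 20:10 and 98% at 10:20 (treated:control), against 94-95% for Welch.

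**5. Where Welch does worse.** With the same all-or-nothing dose and no drug effect (20% transfused in both arms), Student rejects about 4% and Welch about 8% at 20:10, and 5.3% against 5.9% at 18:12. With 10% against 50% transfused, power for Student and Welch is 70% and 64% at 18:12, and 68% and 56% at 20:10. With the splits reversed Welch gains: 67% to 72% at 12:18, and 61% to 69% at 10:20.

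**6. Skewed data.** Assume lognormal data with equal means and SDs of 0.4 and 0.8 of the mean. At 18:12 with the smaller arm more variable, Student rejects 9.5% and Welch 7.9%. Welch is only a partial remedy on a skewed raw scale.

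**The case against.** **If the drug does nothing, there is no problem.** This stands in large part. Randomised arms then share one distribution, and Student's test stays close to its level. A reader might infer that the plan carries a 7-11% risk of declaring an inert drug effective. The documents do not support that: those rates need equal means with unequal SDs. The fixed-dose example cannot supply this, because its means are 2 and 10 cc/kg, so rejection there is correct. For a single dose given or withheld, equal means imply equal SDs. What survives is interval calibration when the drug does act, and protection if it alters spread without altering the mean.

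**The average error is trivial.** It is 5.3-5.7%. But the analysis will be made at one known split, and the average does not calibrate the result at that split.

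**The arms may be 15:15 after all.** The integers 1-30 contain 15 even and 15 odd values, so drawing without repetition and keeping all 30 infants would give exact balance and leave Student near 5%. The text describes the rule only in brief and does not state this. Nor does it say whether the FIBTEM exclusion at rewarming precedes randomization.

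**The variance difference may be small.** Infants under 10 kg receive 200 cc of FFP in the pump prime, and the Schedule of Events footnote on product totals includes the prime. If total FFP counts it, both arms share that variation. For weights assumed uniform over 3-10 kg, the variance of 200/weight is (40,000/7)(1/3 − 1/10) − [(200/7) ln(10/3)]² ≈ 1,333 − 1,183 = 150. The SD ratio then falls from 10/6 = 1.67 to √250/√186 = 1.16. At a ratio of 1.2, Student's rate is only 5.6% at 17:13 and 6.0% at 18:12.

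**Welch is not free everywhere.** This also stands. A reader might infer that Welch can replace Student for every endpoint at almost no cost; step 5 shows otherwise for all-or-nothing volumes.

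**Conclusion.** The concern holds in a conditional form. The plan fixes a pooled-variance test, and its allocation rule, read as independent draws, leaves the arms unequal in about 86% of trials. If the SDs differ by a factor of 1.5 to 2, the standard error is miscalibrated for the split obtained: rejection of equal means is about 7-9% at 18:12 and 3-4% at 12:18 (treated:control, controls more variable). At exactly 15:15, or with equal SDs, little or nothing is wrong.

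The size rests on assumed SD ratios, normal data and two-sided tests, and on reading the allocation rule as it is written. This is a moderate weakness in calibration with an inexpensive repair. It is not evidence of a substantially inflated overall false-positive rate.

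**What to change.** - In Statistical Analyses, replace Student's t-test with Welch's unequal-variance t-test for roughly continuous endpoints: 24-hour blood loss (on a transformed scale, named in advance, if skewed), and hemoglobin and laboratory values at each time point. Make the change in both places where the test is named.
- State that the repeated-measures ANOVA that gates the follow-up tests also pools variances, so changing the follow-up test alone does not remove the assumption.
- For component volumes that are mostly zero or one fixed dose, do not rely on Welch. Specify a permutation (re-randomisation) test that follows the allocation actually used.

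**Cost.** Wording and a short program; no new data. With equal-variance normal data, Welch's power loss is about 0.2 points at 15:15 (75.4% to 75.2% for a 1-SD effect), 0.7-0.8 at 18:12 (73.5% to 72.7% for 1 SD; 78.4% to 77.7% for 1.06 SD) and 1.9 at 20:10 (75.2% to 73.3% for 1.06 SD). The loss is larger, several points, when the smaller arm is the more variable one. Part of Student's apparent advantage there comes from a standard error that is too small.
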